Amgen Proprietary - Confidential

Product: IMLYGIC®

Protocol Number: 20130193
Date: 12 October 2022
Page 3 of 62

Investigator's Agreement

I have read the attached protocol entitled "A Postmarketing Prospective Cohort Study of Melanoma Patients Treated With IMLYGIC® (Talimogene Laherparepvec) in Clinical Practice to Characterize the Risk of Herpetic Infection Among Patients, Close Contacts, and Health Care Providers; and Long-term Safety in Treated Patients", dated 12 October 2022, and agree to abide by all provisions set forth therein.

I agree to ensure that the confidential information contained in this document will not be used for any purpose other than the evaluation or conduct of the clinical investigation without the prior written consent of Amgen Inc.

Signature	
Name of Investigator	Date (DD Month YYYY)
Title:	
Name of Hospital/Site:	
Address/City/State/Country:	
Phone Number:	
Email:	

Protocol Number: 20130193 Date: 12 October 2022

[figure not shown]
Page 4 of 62

Study Design Schema

Follow-up

- observation during and after IMLYGIC® treatment
- during IMLYGIC treatment, study assessments at clinic visits for IMLYGIC treatment
- after discontinuation of IMLYGIC, study assessments every 3 months (± 30 days) via phone or routine clinic visits if they fall within the 30-day window

Collection of data from the following:

^a Median duration of IMLYGIC treatment was approximately 6 months in the clinical trial setting but may differ in clinical practice.

Protocol Number: 20130193

Date: 12 October 2022 Page 5 of 62

Table 1. Schedule of Assessments

	Screening ^a	Baseline	Assessments (approximately every 2 weeks) during IMLYGIC® treatmentb	Assessments (every 3 months ± 30 days) after discontinuation of IMLYGIC ^c
General assessments and medical history				
Written informed consent	х			
Review of eligibility criteria	х			
Patient demographics ^d		x		
Patient characteristics ^e		х		
Medical and surgical history ^f		х		
History of herpetic infection ^g		Х		
Signs and symptoms of herpetic infection ^h			х	х
Results of local laboratory testing of suspicious herpetic lesions for HSV-1, per standard of care	•		At any time –	•
Treatment received				
IMLYGIC ⁱ		X	x	
Other anticancer treatment ^j		X	x	х
Antiherpetic therapy ^k		X	x	х
Assessments of Safety and Survival				
Review of adverse events and serious adverse events during IMLYGIC treatment ^{l, m}		Х	х	

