Review of IMLYGIC-related adverse events and serious adverse events that occur after discontinuation of IMLYGIC ⁿ				Х
Review of product complaints ^o		х	x	
Review of other safety findings ^p		х	х	
Survival assessment ^q			x	х

Page 1 of 2

Footnotes are defined on the next page of this table

Protocol Number: 20130193
Date: 12 October 2022
Page 6 of 62

Table 1. Schedule of Assessments

	Screening ^a	Baseline	Assessments (approximately every 2 weeks) during IMLYGIC® treatment ^b	Assessments (every 3 months ± 30 days) after discontinuation of IMLYGIC ^c		
Results from analysis of samples for talimogene lahe	Results from analysis of samples for talimogene laherparepvec DNA					
Patient ^r	◆ At any time →					
Close contact ^r	← At any time ←					
Health care provider ^r	◆ At any time →					

Page 2 of 2

HSV-1 = herpes simplex virus type 1, HCP = Health care provider, qPCR = quantitative polymerase chain reaction.

- ^a The study site will maintain a screening tally of patients receiving IMLYGIC that includes nonidentifying information about sex, age, **race**, **ethnicity**, and disease stage.
- ^b During IMLYGIC treatment, the study assessments are to be completed at the clinic visits for IMLYGIC treatment.
- ^c After discontinuation of IMLYGIC until the end of follow-up, the study assessments are to be completed every 3 months (± 30 days) via phone or routine clinic visits if they fall within the 30-day window.
- ^d Review the following patient demographics: age, sex, race, and ethnicity.
- e Review the following patient characteristics: Eastern Cooperative Oncology Group (ECOG) performance status and disease stage.
- ^f Review medical and surgical history:
 - surgical therapy
 - radiotherapy
 - local or regional therapy
 - systemic therapy
 - participation in clinical trials
- ⁹ Patient reports the following information on herpetic infections: type of infection, frequency, and testing; type of treatment.
- h Patient reports presence or absence of signs and symptoms of suspected herpetic infection since the time of last observation.
 - Patient's response ("yes" or "no") to the following question will be recorded: "Have you had any signs or symptoms of herpetic infection since your last visit?"

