 - Examples of signs and symptoms include **but not limited to**: pain, burning, or tingling in a blister around the mouth or genitals, fingers, ears, **or any part of the body close to or far from the injection site**; eye pain, light sensitivity, discharge from the eyes, or blurry vision; weakness in arms or legs; extreme drowsiness; mental confusion.
 - If a patient answers "yes", then the following information about the infection will be collected: signs and symptoms, dates, reporting and testing for virus identification, and antiherpetic treatment received.
- Record the following information about IMLYGIC received: dates, dose concentration, injection volume.
- ¹ Record dates and types of other anticancer therapy received (see "f" for the list of therapies).
- ^k Record the following information about antiherpetic therapy received: dates, type (eg, acyclovir, valacyclovir, famciclovir, docosanol), administration route (oral, intravenous, topical).

Protocol Number: 20130193
Date: 12 October 2022
Page 7 of 62

Adverse events and serious adverse events that occur after the patient has signed the informed consent form (ICF) through 30 days after the last dose of IMLYGIC will be recorded in the electronic case report form (eCRF). Adverse events should be assessed on an ongoing basis.

- ^m Safety events which are considered serious must be submitted as individual case safety reports to Amgen via the applicable Amgen Safety Reporting Form (paper or electronic form) within 1 business day of Investigator's awareness.
- ⁿ Adverse events and serious adverse events that occur more than 30 days after the last dose of IMLYGIC and deemed by the Investigator to be related to treatment with IMLYGIC. **Any fatal outcome during long term follow up should be reported as a serious adverse event.**
- ^o Product complaints that occur after the patient has signed the ICF through 30 days after the last dose of IMLYGIC.
- P Other safety findings include, for example, medication errors, exposure to IMLYGIC during pregnancy and breastfeeding, accidental exposure, that occur after the patient has signed the ICF through 30 days after the last dose of IMLYGIC.
- ^q Record the following information on survival status: date of contact, status (eg, alive or deceased), and date and cause of death (if applicable).

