8.2.5 Study Follow-up

The patient's follow-up begins at enrollment and continues through the earliest date of: 5 years after the first IMLYGIC dose, death, withdrawal of consent, or loss to follow-up. Study assessments are detailed in the Table 1. During IMLYGIC treatment, the study assessments for signs and symptoms of herpetic infection, safety, and survival are to be completed at the clinic visits for IMLYGIC treatment. After discontinuation of IMLYGIC until the end of follow-up, these study assessments are to be completed every 3 months (\pm 30 days) via phone or routine clinic visits if they fall within the 30-day window. Data collected will be transcribed into an electronic case report form (eCRF).

At any time that enrolled patients, their close contacts, or their HCPs develop a suspected herpetic lesion, they should seek medical attention to evaluate and swab any suspicious lesion for talimogene laherparepvec DNA testing (per the Postmarketing IMLYGIC Surveillance Program) or wild-type HSV-1 testing (per local standard of care) (Centers for Disease Control, 2010; Patel et al, 2010). The evaluation and reporting of suspected herpetic infections will be done according to the standard of care for IMLYGIC as described in the IMLYGIC USPI and the SmPC. In addition to these materials, for this study, patients will receive an information sheet about the study to share with their close contacts and HCPs. This information sheet will describe the study and will contain the study number for use in reporting a suspected herpetic infection.

For patients enrolled in this study, informed consent will be collected upon study enrollment to link test results from the existing Postmarketing IMLYGIC Surveillance Program to the patient (see Appendix E for a sample laboratory report from Viracor). The results will be captured in the eCRF and be included in the data analysis of the study. For close contacts and HCPs, test results from the Postmarketing IMLYGIC Surveillance Program will be linked to the study only and not to any identifiable patient information, such as the name or date of birth.

Subjects who have ended IMLYGIC treatment and entered into the follow-up period may be allowed to restart treatment if the investigator chooses. In such cases, after restarted IMLYGIC treatment is ended, subjects will continue in the follow-up period as outlined in the schedule of assessments.

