The incidence rate will be summarized for positive tests occurring from the date of first IMLYGIC dose to the date of last IMLYGIC dose + 30 days. If patients receive IMLYGIC over multiple treatment phases, the treatment period is defined as the sum of time from the date of first IMLYGIC dose to 30 days after the date of last IMLYGIC dose or the day before the subsequent treatment phase, whichever comes first, in each treatment phase.

 Incidence rate of herpetic infection with detection of wild-type HSV-1 among patients after discontinuation of IMLYGIC

The incidence rate will be summarized for positive tests occurring from 31 days after the last dose of IMLYGIC through the end of follow-up. If patients receive IMLYGIC over multiple treatment phases, each post-treatment period is defined as sum of time from 31 days after date of last IMLYGIC dose in the prior treatment phase to one day prior to the date of the first IMLYGIC dose in the subsequent treatment phase or the end of study.

Summary of patient characteristics

The following baseline variables will be recorded: sex, age, **race**, **ethnicity**, Eastern Cooperative Oncology Group (ECOG) performance status, and disease stage.

Treatment patterns of anticancer therapy (eg, types and sequence)

Page 23 of 62

footnote "f" in Table 1.

Product: IMLYGIC®

Protocol Number: 20130193 Date: 12 October 2022

For more detail on what types of anticancer therapies will be recorded, please refer to

• Incidence of use of antiherpetic therapy

For more detail on what types of antiherpetic therapy will be recorded, please refer to footnote "k" in Table 1.

 Incidence of adverse events and serious adverse events during treatment with IMLYGIC

Adverse events and serious adverse events (as defined in Section 11) that occur from the date of first IMLYGIC dose to the date of last IMLYGIC dose + 30 days. If patients receive IMLYGIC over multiple treatment phases, the adverse events and serious adverse events collection period is defined as the date of first IMLYGIC dose to 30 days after the date of last IMLYGIC dose or the day before the subsequent treatment phase, whichever comes first, in each treatment phase.

 Incidence of adverse events and serious adverse events related to IMLYGIC after discontinuation of IMLYGIC

Adverse events and serious adverse events (as defined in Section 11) that occur more than 31 days after the last dose of IMLYGIC and attributed to IMLYGIC by the physician.

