10.2 Safety Collection, Recording and Submission to Amgen Requirements

The Investigator is responsible for ensuring that safety events (adverse events, serious adverse events, product complaints, and other safety findings) observed by the Investigator or reported by the patient that occur after signing of the ICF through 30 days after the last dose of IMLYGIC; in addition, safety events (adverse events and serious adverse events) related to IMLYGIC treatment (as deemed by the Investigator) occurring 30 days after the last dose of IMLYGIC through 5 years of follow-up are recorded in the patient's appropriate study documentation. Those safety events which are considered serious must be submitted as individual case safety reports to Amgen via the applicable Amgen Safety Reporting Form (paper or electronic form) within 1 business day of Investigator's awareness. Non-serious Adverse Events must be reported in an expeditious manner, not to exceed 15 calendar days of awareness.

Protocol Exempted Events

One of the objectives of the study is to monitor for long-term safety of IMLYGIC. Hence, adverse events and serious adverse events occurring 30 days after the last dose of IMLYGIC through 5 years after the first IMLYGIC dose and deemed related to IMLYGIC by the Investigator are monitored and reported during the long term follow-up as outlined in Section 10.1. Adverse events and serious adverse events not deemed related to IMLYGIC by the investigator, and products complaints as defined in Section 10.1.4, and other safety findings as defined in Section 10.1.3 such as medication errors, overdose/underdose, misuse, addiction, abuse, off-label use involving IMLYGIC are not monitored during the long term follow-up because IMLYGIC is not administered to patients enrolled during the long-term follow-up phase of the study. Therefore, these other safety events are only monitored and reported during treatment with IMLYGIC and up to the safety visit (ie, up to 30 days after the last dose of IMLYGIC). The pregnancy

Protocol Number: 20130193 Date: 12 October 2022

and lactation cases are monitored during treatment and through 3 months after the last dose of IMLYGIC.

If any of the exempted reportable events during the long-term follow-up have a fatal outcome, they should be considered a serious adverse event and must be collected and reported individually within 1 business day from when the Investigator first becomes aware of the event.

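### Section 10.2 refers to a 30-day safety visit that the schedule does not contain, so adverse events in the 30 days after the last dose must be recorded but have no scheduled review

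*Protocol*

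**What the plan says.** **Section 10.2** ends routine monitoring of unrelated adverse events, product complaints and other safety findings at a named contact: "these other safety events are only monitored and reported during treatment with IMLYGIC and up to the safety visit (ie, up to 30 days after", counted from the final dose.

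**Table 1** has four columns: screening, baseline, on treatment (about every 2 weeks), and every 3 months ± 30 days after discontinuation. Footnote b places the on-treatment work: "During IMLYGIC treatment, the study assessments are to be completed at the clinic visits for IMLYGIC treatment". Section 8.2.5 gives the same two modes of follow-up and continues: "After discontinuation of IMLYGIC until the end of follow-up, these study assessments are to be completed every 3 months", with the same 30-day tolerance.

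**Safety rows in Table 1:**
- The row "Review of adverse events and serious adverse events during IMLYGIC treatment" is marked at baseline and on treatment only. The rows for product complaints and other safety findings are marked the same way.
- The one adverse event row marked after discontinuation is "Review of IMLYGIC-related adverse events and serious adverse events that occur after discontinuation of IMLYGIC". Footnote n limits it to events that "occur more than 30 days after the last dose of IMLYGIC and deemed by the Investigator to be related to treatment with IMLYGIC".

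**The recording duty** is wider than the schedule. Footnote l, on events from consent onward, reads in part "ICF) through 30 days after the last dose of IMLYGIC will be recorded in the electronic case report form (eCRF". It adds that assessment is to be continuous. Section 10.2 makes the investigator responsible for events in that period that are seen by the investigator or told by the patient.

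**The endpoint** in Section 8.3.2.2 counts adverse events and serious adverse events "that occur from the date of first IMLYGIC dose to the date of last IMLYGIC dose + 30 days", whatever their relation to treatment. Section 8.7.2.4.2 analyses the same window.

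**The concern.** The window that the endpoint counts is longer than the period in which the schedule makes anyone ask. A site that works from Table 1 asks about all adverse events at treatment visits, then makes contact about three months later and asks only about related events with onset after day 30. An unrelated or non-serious event on day 10 after the last injection falls outside every scheduled review.

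The stake is the on-treatment adverse event and serious adverse event summary, a secondary safety endpoint in a study set up to characterise safety. Serious or suspected-related events are plausibly more likely to reach the site unprompted than mild or unrelated ones, so any loss could be selective as well as numerical. The same gap applies to product complaints and to other safety findings, which under Section 10.1.3 include transmission of infectious agents and accidental or occupational exposure. Section 8.2.5 allows treatment to be restarted, so the gap can recur after each treatment phase. An analysis plan could not repair it, because it cannot recover events that nobody asked about.

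**Working it through.** There is no figure in the plan to reproduce. The check compares the schedule with the text and then does calendar arithmetic.

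**1. Coverage of days 1 to 30 after the last dose**

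| Source | Covers days 1 to 30? | Scheduled contact? |
|---|---|---|
| Section 8.3.2.2 and 8.7.2.4.2, endpoint | Yes, all events | Not applicable |
| Footnote l and Section 10.2, recording duty | Yes, all events | None given |
| Section 10.2, safety visit | Yes, as the end of monitoring | Named, not in Table 1 or 8.2.5 |
| Table 1, on-treatment rows | Only if a treatment visit falls in the period | Treatment visits |
| Table 1, post-discontinuation adverse event row | No (footnote n: related, onset after day 30) | Every 3 months ± 30 days |

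The empty cells look deliberate: herpetic signs and symptoms, anticancer therapy, antiherpetic therapy and survival are all marked in the post-discontinuation column.

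**2. When the next scheduled contact falls**

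Assumption: discontinuation is dated from the last dose, which the protocol does not define. Three months = 3 × 365.25/12 = 91.3 days.
- Contact window: 91.3 − 30 = 61.3 to 91.3 + 30 = 121.3, about day 61 to 121.
- Time since the 30-day window closed: 61.3 − 30 = 31.3 to 121.3 − 30 = 91.3, about 31 to 91 days.
- Recall for an event on day 30 at the earliest contact: about 31 days. For an event on day 1 at the latest contact: 121.3 − 1 = about 120 days.

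**3. Share of the endpoint window without a scheduled review**

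Formula: uncovered days / (treatment days + 30). The 6-month duration is the trial median in the Study Design Schema footnote, which warns that practice may differ. The 3- and 12-month values are assumed, to show a range.

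| Treatment duration | No visit after last dose |
|---|---|
| 3 months (91.3 days) | 30/121.3 = 25% |
| 6 months (182.6 days) | 30/212.6 = 14% |
| 12 months (365.25 days) | 30/395.25 = 8% |

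If, by assumption, the patient attends one further planned visit 2 weeks after the last dose (the interval in Section 6.1), the uncovered tail is 30 − 14 = 16 days. At 6 months that is 16/212.6 = about 8%.

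For a patient who stops after the second treatment at week 3, the window is 21 + 30 = 51 days. The share is 30/51 = 59% with no further visit, and 16/51 = 31% with one.

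These are shares of calendar time. The protocol gives no adverse event rate for this window, so neither the number nor the share of events missed can be calculated.

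**The case against.** The strongest reply is that collection does not depend on Table 1 contacts at all. Footnote l requires events through day 30 to be entered in the eCRF and assessed continuously, Section 10.2 puts the duty on the investigator, and under Section 8.6.1 the monitor checks eCRF completeness with access to medical records. On this reading the windows agree: the treatment period runs to last dose + 30 days, the related-only row starts after it, and the phrase safety visit is just a loose name for day 30.

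Much of this stands. A reader might infer that these events are in fact under-collected and on-treatment incidence understated. The documents do not support that; they show a duty without a scheduled occasion. What the reply does not remove is that the Section 10.2 duty is worded around events observed or reported, so without a contact, awareness depends largely on the patient coming forward. Footnote h shows that the protocol can write a look-back question, since it asks about herpetic signs since the last observation. None is written for adverse events.

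Two further points stand. The last review need not coincide with the last injection: a patient may attend a planned treatment visit and not be dosed, which shrinks the tail as shown above. And the first post-treatment contact does not ask only about related events. It also collects herpetic symptoms, other therapies and survival with cause of death, and fatal outcomes in long-term follow-up are reportable as serious adverse events.

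**Conclusion.** The inconsistency holds. Section 10.2 relies on a visit that Table 1 and Section 8.2.5 do not schedule, and no scheduled contact asks about all adverse events, product complaints or other safety findings with onset in the 30 days after the last dose, unless a treatment visit happens to fall there. The consequence is a risk of under-ascertainment in the on-treatment adverse event endpoint, of unknown size.

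A reader might take 14% or 59% as the proportion of events lost. That is not supported: both are shares of time and both assume no visit after the last injection. A reader might also extend the gap to the primary endpoint. That is not supported either, because the look-back in footnote h covers the herpetic endpoints.

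The timing rests on dating discontinuation from the last dose; a later date moves the first contact later. The effect is confined to descriptive secondary safety summaries, but the correction is cheap and belongs in the protocol.

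**What to change.** Reconcile Section 10.2, Table 1 and footnotes l and n:
- In Table 1, mark the three rows (adverse events and serious adverse events during treatment, product complaints, other safety findings) at the first post-discontinuation contact after each treatment phase.
- Add a footnote: at this contact, record all events with onset through 30 days after the last dose regardless of relatedness, and related events thereafter. For product complaints and other safety findings, the look-back ends at day 30.
- In Section 10.2, align the phrase safety visit with that contact, and keep the 30-day limit as the onset window rather than the date of a visit.

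The cost is three table marks, one footnote and one phrase, with no new visit. The downside is some added recall: patients would be asked at the 3-month contact about events roughly 1 to 4 months old. Scheduling a phone call just after day 30 would shorten recall, at the price of one extra call per treatment phase.

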10.2.1 Collection of Pregnancy and Lactation Information Female Subjects Who Become Pregnant

Investigator will collect pregnancy information on any female subject who becomes pregnant following exposure to talimogene laherparepvec through 3 months after discontinuing talimogene laherparepvec.

Information will be recorded on the Pregnancy Notification Form (see Appendix D). The worksheet must be submitted to Amgen Safety within 1 business day of when investigator first becomes aware of the subject's pregnancy (Note: investigator is not required to provide any information on the Pregnancy Notification Form that violates the country or regions local privacy laws).

After receipt of the Pregnancy Notification Form, Amgen Safety will provide Investigator with a consent form and questionnaire to collect additional information. After obtaining the female subject's signed consent for release of pregnancy and infant health information, the investigator will collect pregnancy and infant health information and complete the pregnancy questionnaire for any female subject who becomes pregnant following exposure to talimogene laherparepvec through 3 months after discontinuing of the talimogene laherparepvec. This information will be forwarded to Amgen Safety. Generally, infant follow-up will be conducted up to 12 months after the birth of the child (if applicable).

Any termination of pregnancy will be reported to Amgen Safety, regardless of fetal status (presence or absence of anomalies) or indication for procedure.

While pregnancy itself is considered another safety finding, any pregnancy complication or report of a congenital anomaly or developmental delay, fetal death, or suspected adverse reactions in the neonate will be reported as an adverse event or serious adverse event. Note that an elective termination with no information on a fetal congenital malformation or maternal complication is generally not considered an adverse event, but still must be reported to Amgen as a pregnancy exposure case.

If the outcome of the pregnancy meets a criterion for immediate classification as a serious adverse event (eg, female subject experiences a spontaneous abortion, stillbirth, or neonatal death or there is a fetal or neonatal congenital anomaly) the Investigator will report the event as a serious adverse event.

Page 38 of 62

Male Subjects with Partners who Become Pregnant [or Were Pregnant at the Time of Enrollment]

In the event a male subject fathers a child following exposure to talimogene laherparepvec, and for an additional 3 months after discontinuing talimogene laherparepvec, the information will be recorded on the Pregnancy Notification Form.

The form (see Appendix D) must be submitted to Amgen Safety within 1 business day of when the Investigator first becomes aware of the pregnancy. (Note: Investigator is not required to provide any information on the Pregnancy Notification Form that violates the country or regions local privacy laws).

After receipt of the Pregnancy Notification Form, Amgen Safety will provide Investigator with a consent form and questionnaire to collect additional information. The Investigator will attempt to obtain a signed consent for release of pregnancy and infant health information directly from the pregnant female partner to obtain additional pregnancy information.

After obtaining the female partner's signed consent for release of pregnancy and infant health information, the Investigator will collect pregnancy outcome and infant health information on the pregnant partner and her baby and complete the pregnancy questionnaires. This information will be forwarded to Amgen Safety.

Generally, infant follow-up will be conducted up to 12 months after the birth of the child (if applicable).

Any termination of the pregnancy will be reported to Amgen Safety regardless of fetal status (presence or absence of anomalies) or indication for procedure.

Collection of Lactation Information

Investigator will collect lactation information on any female subject who breastfeeds while taking talimogene laherparepvec through 3 months after discontinuing talimogene laherparepvec.

Information will be recorded on the Lactation Notification Form (see Appendix **D**) and submitted to Amgen Safety within 1 business day of when the Investigator first becomes aware of the lactation exposure.

With the female subject's signed consent for release of mother and infant health information, the Investigator will collect mother and infant health information and complete the lactation questionnaire on any female subject who breastfeeds while taking

Protocol Number: 20130193
Date: 12 October 2022
Page 40 of 62

talimogene laherparepvec through 3 months after discontinuing talimogene laherparepvec.

